17. QUALITY OF LIFE ANALYSIS

Not applicable.

18. SAFETY OUTCOMES

All outputs for safety outcomes will be based on the Safety Analysis Set. Percentages will be computed on the total number of subjects in each treatment group.

18.1. ADVERSE EVENTS

Adverse Events (AEs) will be coded using MedDRA central coding dictionary, Version 20.1.

An AE is defined as any untoward medical occurrence in a patient or clinical investigation patient administered a pharmaceutical product that does not necessarily have a causal relationship with the product. An AE can therefore be any unfavorable and unintended sign (including a new, clinically important abnormal laboratory finding), symptom, or disease, temporally associated with drug administration, whether or not related to the product.

The above definition covers also cases of:

Exacerbation of pre-existing diseases or conditions.

Pre-existing diseases or conditions (reported at time of screening in medical history) will not be

Document: \sasdata\Mylan\Insulin_glargine\SYA22825\Biostatistics\Documentation\SAP\MYL-1501D-3004_SAP_Final_2_0_clean.doc

Author: [name]

Version Number:

2.0

Version Date:

18OCT2018

Template No: CS_TP_BS016 Revision 4
Effective Date: 01Apr2016

Reference: CS_WI_BS005

Analysis Plan Template

considered AEs unless there is an increase in the frequency or severity, or a change in the quality of the disease or condition.

Events occurring in patients treated with the active comparator are also considered AEs.

An AE will be defined as treatment emergent (TEAE) if the first onset (or worsening in the case of pre-existing disease) is after randomization through follow-up visit or 14 days after last dose [for patients that do not have a follow-up visit].

See [Appendix 1](#) for handling of partial dates for AEs. In the case where it is not possible to define an AE as treatment emergent or not, the AE will be classified by the worst case; i.e. treatment emergent.

An overall summary of number of patients within each of the categories described in the sub-sections below, will be provided as specified in the templates.

Treatment group comparison will be performed using Fisher's exact test. P-value for the corresponding two-sided test will be presented.

Listings will include TEAEs and Non-TEAEs.

18.1.1. ALL TEAEs

Incidence of TEAEs will be presented by System Organ Class (SOC) and Preferred Term (PT) and also broken down further by maximum severity and relationship to study medication. The number of events will also be presented.

18.1.1.1. Severity

Severity is classed as mild/ moderate/ severe/ life-threatening/ death (increasing severity). TEAEs starting on or after the first dose of study medication with a missing severity will be classified as severe. If a patient reports a TEAE more than once within that SOC/ PT, the AE with the worst case severity will be used in the corresponding severity summaries.

18.1.1.2. Adverse Drug Reaction (Relationship to Study Medication)

All noxious and unintended responses to an investigational product related to any dose of the investigation products should be considered adverse drug reactions (ADRs). The phrase "responses to an investigational product" means that a causal relationship between an investigational product and an AE is at least a reasonable possibility. All AEs judged by either the reporting investigator or the sponsor as having a reasonable causal relationship to an investigational product will be designated as ADRs.

All AEs, with the causal relationship to the trial drug reported as "possible", "probable" or "definite" will be considered ADRs. If the relationship to the trial drug is not given, then the AE must be treated as if the relationship were "possible".

If a patient reports the same AE more than once within that SOC/PT, the AE with the worst case relationship to study medication will be used in the corresponding relationship summaries.

Frequency and percentage of patients having adverse drug reaction will be presented by treatment,

Document:	\sasdata\Mylan\Insulin_glargine\SYA22825\Biostatistics\Documentation\SAP\MYL-1501D-3004_SAP_Final_2_0_clean.doc		
Author:	[name]	Version Number:	2.0
		Version Date:	18OCT2018
Template No:	CS_TP_BS016 Revision 4	Reference:	CS_WI_BS005
Effective Date:	01Apr2016		

Analysis Plan Template

SOC and PT.

18.1.2. TEAEs LEADING TO DISCONTINUATION OF STUDY MEDICATION

TEAEs leading to permanent discontinuation of study medication will be identified by using the Treatment withdrawn field in the CRF under “Action taken with study medication”.

For TEAEs leading to discontinuation of study medication, summaries of incidence rates (frequencies and percentages) by SOC and PT will be prepared.

18.1.3. SERIOUS ADVERSE EVENTS

Serious adverse events (SAEs) are those events recorded as “Serious” on the Adverse Events page of the (e)CRF. A summary of serious TEAEs by SOC and PT will be prepared.

18.1.4. ADVERSE EVENTS LEADING TO DEATH

TEAEs leading to Death are those events which are recorded as “Fatal” on the Adverse Events page of the (e)CRF. A summary of TEAEs leading to death by SOC and PT will be prepared.

18.1.5. LOCAL OR SYSTEMIC ALLERGIC REACTION

The local and systemic allergic reactions are recorded on the adverse events page of the eCRF.

TEAE incidence of both local and systemic allergic reaction will be summarized by SOC and treatment group. A separate listing will also be produced which include only events of local or systemic allergic reaction.

18.1.6. DEVICE-RELATED ASSESSMENT

The relationship to the insulin glargine pen/needle and to the Humalog pen/needle are recorded on the adverse events page of the eCRF.

TEAE incidence will be summarized by SOC and treatment group for the insulin glargine pen/needle relationship and for the humalog pen/needle relationship and for both.

The incidence of device problems (even if not leading to an AE) will be summarized for each treatment group.

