6.5.2.2.1 Classification

A. Severe Hypoglycemia

An event is considered as severe hypoglycemia if it requires the assistance of another person to actively administer carbohydrate, glucagon, or other resuscitative actions which results in neurological recovery, regardless of the availability of a blood glucose measurement. These episodes may be associated with sufficient neuroglycopenia to induce seizure or coma. Plasma glucose measurements may not be available during such an event, but neurological recovery attributable to the restoration of normal plasma glucose is considered sufficient evidence that the event was induced by a low plasma glucose concentration.

B. Documented Symptomatic Hypoglycemia

An event during which typical symptoms of hypoglycemia are accompanied by a measured plasma glucose concentration ≤ 70 mg/dL (3.9 mmol/L).

C. Asymptomatic Hypoglycemia

An event not accompanied by typical symptoms of hypoglycemia but with a measured plasma glucose concentration ≤ 70 mg/dL (3.9 mmol/L).

D. Probable Symptomatic Hypoglycemia.

Characteristic symptoms of hypoglycemia with no blood glucose level measurement that resolved with food intake, subcutaneous glucagon, or intravenous glucose.

E. Relative Hypoglycemia.

An event during which the subject reports any of the typical symptoms of hypoglycemia, and interprets the symptoms as indicative of hypoglycemia, but with a measured plasma glucose concentration > 70 mg/dL (3.9 mmol/L).

F. Nocturnal Hypoglycemia.

Nocturnal hypoglycemia will include hypoglycemia that occurs from the time the subject goes to bed at night till the time he or she wakes up. This may include any of the above 5 types of hypoglycemia.

Note: A diagnosis of severe hypoglycemia as per above classification will always be considered as serious adverse event. Other hypoglycemic episodes which fulfils ICH criteria for seriousness (life-threatening, hospitalization etc.) or represent important medical events based on investigator's judgment should also be reported to sponsor within 24 hours.

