6.5.2.2.4 Reporting of hypoglycemic episodes

Hypoglycemic events and any associated symptoms are recorded only on the hypoglycemic episodes page of the CRF. Severe hypoglycemia and those episodes meeting any of the ICH

seriousness criteria ([Section 9.2.4](#)) are also to be notified as SAEs to the Mylan Global Product Safety and Risk Management department, as described in [Section 9.3.2.8](#); and entered on the SAE and AE pages.

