7.3 Secondary Endpoints

The following efficacy measures (both actual and change values) will be summarized at baseline and scheduled visit. Similar statistical analysis approach for primary will be performed for continuous variables without imputing missing values. Contrasts of LS mean at each scheduled visit will be used to evaluate all pairwise treatment comparisons, and 95% confidence intervals for treatment differences in LS means will be computed for each visit.

- Change in fasting plasma glucose from baseline
- Change in basal insulin, meal-time, and total insulin dose per unit body weight (U/kg) from baseline
- Change in 8-point SMBG profile from baseline.

All above analyses will be performed on ITT set.

The following safety measures (both actual and change values) will be summarized at baseline and scheduled visit. Contrasts of LS mean at each scheduled visit will be used to evaluate all pairwise treatment comparisons, and 95% confidence intervals for treatment differences in LS means will be computed for each visit. For categorical data analyses, Fisher's exact test or Chi-squared test will be used. The details will be provided in the SAP.

- Incidence of positive antibody response and change in antibody percentage binding from baseline.
- Change in hypoglycemia rate (30 day adjusted) from baseline and incidence of hypoglycemic events
- Incidence of treatment-emergent adverse events (TEAEs) and serious adverse events (SAEs)
- Incidence of local allergic reactions, systemic allergic reactions and other adverse events
- Incidence of device-related safety assessment

The incidence of subjects with each of the three following criteria will be summarized descriptively (for categorical measures) by treatment to explore possible insulin neutralization effect:

- An increase of over 10% in cross reacting antibodies from baseline
- Increases in HbA1c of over 0.2% from baseline at any visit
- Increase in total or basal insulin dose at any visit

The total incidence of Device-related safety events will be summarized for each treatment group and would include device-related TEAEs and events related to device complaints or failures. For device-related TEAEs, two categories will be summarized for each treatment: needle-related TEAEs such as pain, bruise, and bleeding; and other device-related TEAEs, such as hyperglycemia or hypoglycemia. For confirmed device-related malfunctions or failures, incidence will be listed and summarized for each treatment.

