9.3.2.2 Action Taken

The possible actions taken for an AE are described in Table 6.

Table 6: Action Taken for an Adverse Event

Dose reduced	The dose regimen was reduced by changing its frequency, strength, or amount.
Dose increased	The dose regimen was increased by changing its frequency, strength, or amount.
Treatment interrupted	The treatment was temporarily interrupted.
Treatment withdrawn	The treatment was permanently discontinued.
Concomitant therapy or procedures	Treatment was needed as a result of the AE (the concomitant treatment should be recorded on the relevant page of the CRF).
Unknown	Not known, not observed, not recorded, or refused.
No action taken	The AE did not require any intervention.
Not applicable	AE occurred after study medication was permanently withdrawn or subject completed the treatment period.

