9.3.2.5 Documentation

All AEs occurring within the period of observation for the study must be documented in the CRF with the following information; where appropriate (the period of observation for the study is described in [Section 6](#)):

- AE name or term in standard medical terminology.
- When the AE first occurred (start date and time); SAE start date is defined as the date the AE became serious.
- When the AE stopped (stop date and time or date and time of last observation if ongoing, i.e., recovering or not recovered).
- Severity of the AE.
- Seriousness criteria (hospitalization, death, etc.).
- Action taken with study medication as a result of AE.
- Outcome.
- Investigator’s opinion regarding the AE relationship to the study treatments.

Hypoglycemic events and associated signs/symptoms will only be recorded on the hypoglycemic episodes page of the CRF, unless they are SAEs (i.e., a severe episode).

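### Non-serious hypoglycemia attributed to the pen or needle has no route into the device-related TEAE table, although protocol 7.3 names hypoglycemia as an example for that table

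*SAP*

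**What the plan says.** Device-related safety is a listed objective (protocol V2.0, 3.1.2) and a listed secondary safety endpoint (3.2.2.1). Protocol 7.3 splits device-related TEAEs into needle-related events and "other device-related TEAEs, such as hyperglycemia or hypoglycemia". It also counts events tied to device complaints or failures.

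Protocol 6.5.2.2.4 sets the recording rule: "Hypoglycemic events and any associated symptoms are recorded only on the hypoglycemic episodes page of the CRF". Severe episodes and those meeting a seriousness criterion are entered on the SAE and AE pages as well. Section 9.3.2.5 repeats the rule and its exception: such events "will only be recorded on the hypoglycemic episodes page of the CRF, unless they are SAEs (i.e., a severe episode").

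SAP V2.0 section 18.1.6 states that "The relationship to the insulin glargine pen/needle and to the Humalog pen/needle are recorded on the adverse events page of the eCRF". It summarises TEAE incidence by system organ class and arm for the glargine pen or needle, the Humalog pen or needle, and both. It separately counts device problems whether or not an AE followed. SAP 18.6.2 analyses hypoglycemia by type and by 30-day rate. SAP 4.3 reports no changes from the protocol.

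For discontinuation, SAP 18.1.2 says that "TEAEs leading to permanent discontinuation of study medication will be identified by using the Treatment withdrawn field in the CRF under" the heading for action taken with study medication.

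**The concern.** The protocol names hypoglycemia as something the device table should show. The recording rule and the SAP's choice of source together leave the non-serious episodes out. A reader who sees few hypoglycemia entries in that table could take this as evidence about the pen, when it may only reflect which CRF page feeds the table.

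What is at stake is a reported secondary safety endpoint, not the non-inferiority conclusion. Hypoglycemia as such is not lost: every type is recorded, rates are modelled by arm, and episodes are listed. What the plan does not provide is the link between a device fault and a non-serious episode.

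**Working it through.** No arithmetic applies. The check traces which record feeds which table, using protocol V2.0 and SAP V2.0.

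1. **What the device table should contain.** Protocol 7.3: hypoglycemia is a named example in the second device category.
2. **Where hypoglycemia is recorded.** Protocol 6.5.2.2.4 and 9.3.2.5: on its own page only, unless serious. Section 6.5.2.2.1 adds: "A diagnosis of severe hypoglycemia as per above classification will always be considered as serious adverse event". Severe episodes therefore always reach the AE page.
3. **Where the SAP looks for attribution.** SAP 18.1.6 names the AE page and no other.
4. **Whether the hypoglycemia analysis fills the gap.** SAP 18.6.2 uses symptoms, glucose value, need for assistance and nocturnal timing. It uses no device field.
5. **Whether the hypoglycemia record is said to hold attribution.** The items listed in protocol 6.5.2.2.3 cover timing, remedies, symptoms, glucose values and subtype. Neither device relationship nor action taken with study drug is among them.
6. **Whether another record joins fault and episode.** The device-problem count (SAP 18.1.6) shows the fault without its clinical consequence. The minimum complaint report (protocol 5.2) asks only whether an SAE resulted. Dosing errors go to protocol deviations (9.4.2). No stated step connects these.

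| Event | Device-related TEAE table (18.1.6) | Device-problem count (18.1.6) | Hypoglycemia analysis (18.6.2) |
|---|---|---|---|
| Severe or other serious hypoglycemia attributed to pen or needle | Counted | Fault counted if reported | Counted |
| Non-serious hypoglycemia attributed to pen or needle | Not counted | Fault counted if reported | Counted, without attribution |

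**Categories.** Protocol 7.3 has a needle-related and an other category. SAP 18.1.6 has neither, and SAP 4.3 does not list the omission.

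**Discontinuation table.** SAP 18.1.2 refers to the CRF and names no page. Protocol 9.3.2.2 treats action taken as an attribute of an AE: "The possible actions taken for an AE are described in Table 6". Section 9.3.2.5 lists it among the items documented for each AE. The likely reading is that the field sits on the AE page, so a non-serious hypoglycemia that led to withdrawal of study drug would be missed. This is an inference, unlike the device result.

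**The case against.** Several points on the other side stand.

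- **The eCRF is not in the documents.** The list in protocol 6.5.2.2.3 describes episode documentation and is not a CRF specification. The AE and hypoglycemia row of the schedule of activities mentions medication, pen or needle as the cause, so an attribution field may exist. The supportable statement is that the SAP uses no such field. A reader might infer that all non-serious device-related hypoglycemia is missing from the data; the documents do not show that.
- **A reported fault is not invisible.** It enters the device-problem count, and protocol 7.3 includes complaints and failures in total device incidence. What is lost is the episode's classification as a device-related TEAE.
- **The discontinuation table is less exposed.** A reader might infer that both safety tables miss the event they most need. The withdrawal criterion in protocol 4.2.3 gives severe hypoglycemia and hypoglycemic unawareness as examples, and severe episodes reach the AE page. SAP 10 also summarises reasons for discontinuation by arm, though not as TEAEs by preferred term.
- **The stakes should not be inflated.** Nothing in the documents ranks hypoglycemia from dosing error as the main device risk, and both arms use an identical pen presentation (protocol 2.2).
- **The SAP may alter non-primary plans.** Protocol section 7 allows this, and SAP 9 leaves table layout to templates that are not in the documents. The omission of the two categories is therefore permissible, but it should be declared.

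None of this removes the conflict between protocol 7.3 and the route that the recording rule and SAP 18.1.6 lay down together.

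**Conclusion.** The device point holds. Following the current plan, hypoglycemia that is neither severe nor otherwise serious is not counted as a device-related TEAE, even when pen or needle caused it. Serious and severe episodes are counted. The undeclared omission of the two protocol categories is a separate, smaller fault, and it stands whatever fields the eCRF contains.

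The discontinuation point is a secondary clarification, because it depends on reading the action-taken field as belonging to the AE page.

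The number of affected events cannot be given: no event rates are stated and the eCRF cannot be inspected. The effect may be small. The primary HbA1c analysis does not depend on any of these records.

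**What to change.** **SAP 18.1.6.** State whether pen or needle relationship is collected on the hypoglycemia page.

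- If it is, or if the field can be added, count attributed hypoglycemia from both pages, counting once any episode entered on both.
- If not, footnote the table as excluding non-serious hypoglycemia. Add a supportive listing that matches device problems to hypoglycemia episodes by subject and date. Complaint reports carry a date of occurrence and episode records carry date and time, so matching is feasible. Label the listing as temporal association, not attribution.

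**Categories.** Restore the needle-related and other categories of protocol 7.3, or declare their removal in SAP 4.3.

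**SAP 18.1.2.** Name the page that holds the action-taken field. If it is the AE page, count non-serious hypoglycemia leading to withdrawal of study drug from the hypoglycemia page where recorded, or footnote its exclusion.

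**Cost.** SAP wording, plus a field or a modest linkage step. The pooled-site table in SAP 8.2 already lists 13 + 9 + 13 + 19 + 16 + 9 + 10 + 12 + 29 + 37 + 13 + 8 + 23 + 8 = 219 subjects against 202 planned, so a field added now would probably rest on retrospective attribution. In that case the footnote and listing are the safer choice. Entering non-serious episodes on the AE page instead would contradict protocol 6.5.2.2.4 and 9.3.2.5 and would need a protocol amendment.

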18.1.7. NON TEAEs

The non-TEAEs, the events occurred during the run-in phase before randomization, will be summarized separately. The frequency and percentage of patients experiencing non-TEAEs, serious non-TEAE, withdrawing during the run-in phase due to non-TEAE during run-in phase,

Document:	\sasdata\Mylan\Insulin_glargine\SYA22825\Biostatistics\Documentation\SAP\MYL-1501D-3004_SAP_Final_2_0 clean.doc		
Author:	[name]	Version Number:	2.0
		Version Date:	18OCT2018
Template No:	CS_TP_BS016 Revision 4	Reference:	CS_WI_BS005
Effective Date:	01Apr2016		

Analysis Plan Template

Deaths before the active treatment start will be summarized. All enrolled patients who enter into the run-in period will be considered for this summary.

18.2. LABORATORY EVALUATIONS

Results from the central laboratory will be included in the reporting of this study for Hematology, Blood Chemistry and Urinalysis. A list of laboratory assessments to be included in the outputs is included in the [protocol section 6.5.2.3](#).

Presentations will use SI Units as provided by the central laboratory Q2.

Quantitative laboratory measurements reported as "< X", i.e. below the lower limit of quantification (BLQ), or "> X", i.e. above the upper limit of quantification (ULQ), will be converted to X for the purpose of quantitative summaries, but will be presented as recorded, i.e. as "< X" or "> X" in the listings.

The following summaries will be provided for laboratory data:

- Actual and change from baseline by visit (for quantitative measurements). Descriptive summaries will be presented for the actual and the changes from baseline at each visit. Changes from baseline will be analyzed using the same MMRM model then the primary efficacy variable, but without any imputation. LSMeans for each treatment group and associated SE/2-sided 95% CI will be presented. Differences in LSMeans will also be calculated with the SE, 2-sided 95% CI and p-value.
- Incidence of markedly abnormal laboratory criteria. The number of patients and percentages will be provided for each treatment group at each visit for each markedly abnormal criteria.
- Shift from baseline according to normal range criteria (for quantitative measurements and categorical measurements)

18.2.1. LABORATORY REFERENCE RANGES AND MARKEDLY ABNORMAL CRITERIA

Quantitative laboratory measurements will be compared with the relevant laboratory reference ranges in SI units and categorized as:

- Low: Below the lower limit of the laboratory reference range.
- Normal: Within the laboratory reference range (upper and lower limit included).
- High: Above the upper limit of the laboratory reference range.

The markedly abnormal criteria are defined in the [table](#) below:

Document:	\sasdata\Mylan\Insulin_glargine\SYA22825\Biostatistics\Documentation\SAP\MYL-1501D-3004_SAP_Final_2_0_clean.doc		
Author:	[name]	Version Number:	2.0
		Version Date:	18OCT2018
Template No:	CS_TP_BS016 Revision 4	Reference:	CS_WI_BS005
Effective Date:	01Apr2016		

Analysis Plan Template

Laboratory Category	Parameter (unit)	Markedly Abnormal Low	Markedly Abnormal High
Hematology	WBC(X10E3 cells/μl)	<2.0	>20.0
	Neutrophil count (X10E3 cells/μl)	<1.0	NA
	Hemoglobin (g/dL)	<8.0	>20
	Platelets(cells/μl)	<50	>999
Biochemistry	ALT	NA	>3XULN
	AST	NA	>3XULN
	ALK phosphatase	NA	>3XULN
	Total Bilirubin	NA	>2XULN
	LDH (IU/L)	NA	>800
	Glucose (mg/dL)	<55	>270
	Creatinine	NA	>1.5XULN
	BUN (mg/dL)	NA	>60
	CPK(U/L)	NA	>850
	Sodium (mEq/L)	<130	>155
	Potassium(mEq/L)	<3.0	>6.0
	Total Protein(g/dL)	NA	>9.5

Document: \sasdata\Mylan\Insulin_glargine\SYA22825\Biostatistics\Documentation\SAP\MYL-1501D-3004_SAP_Final_2_0_clean.doc

Author: [name]

Version Number:

2.0

Version Date:

18OCT2018

Template No: CS_TP_BS016 Revision 4
Effective Date: 01Apr2016

Reference: CS_WI_BS005

Analysis Plan Template

Laboratory Category	Parameter (unit)	Markedly Abnormal Low	Markedly Abnormal High
	Albumin(g/dL)	<2.0	NA
	Calcium (mg/dL)	<7.0	>12.5
	Lipase(U/L)	NA	>180
Lipids	Triglycerides (mg/dL)	<10	>900
	Total Cholesterol (mg/dL)	<20	>400
	LDL Cholesterol (mg/dL)	<20	>350
	HDL Cholesterol (mg/dL)	<20	NA

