6.5.2.3 Laboratory Safety

The following safety laboratory tests will be performed at times defined in the study schedules in [Sections 1](#) and [Section 6](#).

Table 4: Laboratory Safety Tests

Hematology	Chemistry	Urinalysis	Other
Hemoglobin	Urea and Creatinine	pH	Urine hCG
Hematocrit	Glucose	Glucose (qual)	HIV and HBsAg and
RBC count	Calcium	Protein (qual)	HCVAb
Platelet count	Sodium	Blood (qual)	HbA1c
WBC count	Potassium	Ketones	
Total neutrophils (Abs)	Chloride	Nitrites	
Eosinophils (Abs)	AST, ALT	Leukocyte esterase	
Monocytes (Abs)	Total Bilirubin	Microscopy/culture ^a	
Basophils (Abs)	Direct/Indirect bilirubin		
Lymphocytes (Abs)	Alkaline phosphatase		
	Uric acid		
	Albumin		
	Total protein		
	CRP		
	C-Peptide		
	Lipid Profile		

^a Only if urine dipstick is positive for blood, protein, nitrites or leukocyte esterase.

Hematology and chemistry will be analyzed by central laboratory. Urinalysis will be conducted by dipstick at site and if urine is positive for blood, protein, nitrites, or leukocyte esterase, will be analyzed via microscopy/culture by a central laboratory.

Blood volumes to be collected and blood and urine sample handling instructions will be provided in the central vendor laboratory manual. The central laboratory will provide collection materials and directions for packaging and shipment of samples.

Any clinically significant findings in laboratory safety data should be recorded as an AE. Determination of clinical significance and seriousness will be based on the Investigator's medical judgment.

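### The platelet limits for marked abnormality (<50, >999) are labelled cells/µl without the X10E3 multiplier, so the written criterion is wrong by a factor of 1,000

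*SAP*

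**What the plan says.** SAP V2.0 section 18.2.1 tabulates low and high limits for marked laboratory abnormality. The first two hematology rows are headed "WBC(X10E3 cells" per µl (limits <2.0 and >20.0) and "Neutrophil count (X10E3 cells" per µl (limit <1.0). The platelet row is headed only "Platelets(cells" per µl, with limits <50 and >999. SAP V1.0 section 18.2.1 prints the same platelet row, and the V2.0 version history lists no change to it.

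Section 18.2 puts the limits to use: "The number of patients and percentages will be provided for each treatment group at each visit for each markedly abnormal criteria". Platelets are among the tests reported, because the hematology column of protocol Table 4 (section 6.5.2.3) lists "Platelet count". On units, section 18.2 says: "Presentations will use SI Units as provided by the central laboratory Q2". Neither section gives a platelet unit or a conversion that would override the row label.

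**The concern.** A marked-abnormality limit is a number together with its unit. Here the numbers fit counts in thousands per µl, but the label says single cells per µl. The two neighbouring cell-count rows carry the multiplier, and the omission recurs in both SAP versions, so it does not look like a loss in converting the PDF to text.

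The limits are the operative rule for a prespecified safety table. A programmer who converts platelet results to the stated unit and applies the stated limits would classify essentially every subject as markedly high at every visit. Nobody could be classified as markedly low, and a truly low count would be flagged in the wrong direction. A programmer who silently repairs the unit would get a sensible table that departs from the signed plan without any record.

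**Working it through.** This is a unit check. No sample size, power or alpha figure is involved.

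**Inputs.** From SAP V2.0 section 18.2.1:
- platelets <50 and >999 cells/µl;
- WBC <2.0 and >20.0 ×10^3 cells/µl;
- neutrophils <1.0 ×10^3 cells/µl.

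Assumption: platelet counts lie between 1,000 and 1,200,000 cells/µl. The documents give no platelet range, so a deliberately wide one is used.

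**Step 1: put the cell-count rows in one unit (cells/µl).**
- WBC low: 2.0 × 1,000 = 2,000. WBC high: 20.0 × 1,000 = 20,000.
- Neutrophil low: 1.0 × 1,000 = 1,000.
- Platelets as printed: low 50, high 999.

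The printed platelet high limit (999) lies below the table's own low limits for WBC (2,000) and for neutrophils (1,000).

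**Step 2: restore the multiplier.** 50 × 1,000 = 50,000 and 999 × 1,000 = 999,000 cells/µl.

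**Step 3: apply both readings to assumed counts.** The printed rule is low if the count is <50 and high if it is >999. The thousands reading is low if count/1,000 is <50 and high if count/1,000 is >999.

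| Count (cells/µl) | As printed | Read as X10E3 |
|---|---|---|
| 1,000 | high | low |
| 20,000 | high | low |
| 49,000 | high | low |
| 50,000 | high | none |
| 150,000 | high | none |
| 400,000 | high | none |
| 999,000 | high | none |
| 1,200,000 | high | high |

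As printed, a count escapes the high flag only if it is 999 cells/µl or less, and it is flagged low only below 50 cells/µl. Across the assumed range all counts are flagged high and none low.

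**Step 4: equivalence with the SI unit.** One litre is 10^6 µl, so 10^3 cells/µl = 10^3 × 10^6 = 10^9 cells/L. A result in 10^9/L has the same numerical value as one in X10E3 cells/µl, so 50 and 999 applied directly to 10^9/L data give the right-hand column.

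**The case against.** The strongest reply is that the output may never go wrong. Section 18.2 says that presentations use the central laboratory's SI units. If platelets arrive in 10^9/L and the program compares those values with 50 and 999, the flags are as intended (step 4). That stands, and the cause is probably just a missing multiplier in a label.

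It does not rescue the written criterion, because comparing printed numbers directly with SI values is not a rule that works for the whole table. The glucose limits are 55 and 270 mg/dL, while SAP section 11 reports baseline fasting plasma glucose in mmol/L. Using the protocol's own pairing of 70 mg/dL with 3.9 mmol/L (section 6.5.2.2.1), the limits are 55 × 3.9/70 ≈ 3.1 and 270 × 3.9/70 ≈ 15.0 mmol/L. Compared without conversion, a glucose of 10 mmol/L would fall below 55 and be flagged low. Glucose needs its printed unit to be honoured; doing the same for platelets gives the wrong answer.

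A reader might draw three stronger conclusions, which the documents do not support.

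- *The trial could not detect low platelets.* Section 18.2 also plans by-visit summaries, an MMRM on change from baseline and shifts against laboratory reference ranges. Protocol section 6.5.2.3 has clinically significant laboratory findings recorded as adverse events. Low counts would appear there. The marked-abnormality criteria feed only counts and percentages: section 18.2 attaches no test to them, and SAP section 5.1 plans no DMC or interim analysis.
- *The other limits are wrong because they are not in SI units.* A limit printed with its correct unit converts exactly. Of the 22 other rows, 12 are in mg/dL, g/dL or mEq/L. Sodium and potassium have the same value in mmol/L, which leaves 10 needing a conversion. Five other rows are multiples of the upper limit of normal and need none.
- *The LDH, CPK and lipase rows are an error with consequences.* These tests are absent from protocol Table 4, but section 18.2 takes the tests to be output from that protocol section. The three rows should therefore produce nothing.

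**Conclusion.** The point holds in a narrow form. The platelet criterion in SAP V2.0 section 18.2.1 is wrong as written by a factor of 1,000. Followed literally, it flags every count in the assumed range of 1,000 to 1,200,000 cells/µl as markedly high and none as markedly low. The result depends only on platelet counts being at least 1,000 per µl, which the documents do not state.

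The damage is limited to one descriptive safety table, and it arises only if the printed unit is honoured. It does not reach the primary analysis, the other platelet outputs or adverse event reporting. It is still more than a slip in background text, because the row is the operative definition for a prespecified count by arm and visit. It is worth correcting on that ground alone.

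**What to change.** In SAP V2.0 section 18.2.1, print the platelet unit as X10E3 cells/µl, or equivalently 10^9/L if the table is to match the laboratory's SI reporting. Leave 50 and 999 unchanged; no clinical threshold is altered. Check that the program for the markedly abnormal table compares like units for this row, and note the correction in the version history so that the output and the plan agree.

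The cost is an edit to one table cell and a brief program check, with no new data. Restating the other limits in SI units and removing the LDH, CPK and lipase rows are optional tidying and not part of this correction.
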